If the outcome of the pregnancy meets the criteria for immediate classification as a SAE (i.e., spontaneous abortion [any congenital anomaly detected in an aborted fetus is to be documented], stillbirth, neonatal death, or congenital anomaly), the Investigator should follow the procedures for reporting SAEs (i.e., report the event to Celgene Corporation Worldwide Drug Safety Surveillance (WWDSS) by facsimile within 24 hours of the Investigator's knowledge of the event) and report the event to MDACC IRB and ORERM.

Any suspected fetal exposure to lenalidomide must be reported to Celgene, MDACC IRB AND ORERM within 24 hours of being made aware of the event. The patient should be referred to an obstetrician/gynecologist experienced in reproductive toxicity for further evaluation and counseling.

All neonatal deaths that occur within 30 days of birth should be reported, without regard to causality, as SAEs. In addition, any infant death after 30 days that the Investigator suspects is related to the *in utero* exposure to lenalidomide should also be reported. In the case of a live "normal" birth, Celgene Corporation Worldwide Drug Safety Surveillance (WWDSS), MDACC IRB AND ORERM should be advised as soon as the information is available.

Celgene Drug Safety Contact Information:

Celgene Corporation Worldwide Drug Safety Surveillance (WWDSS) [name]

Toll Free: [contact] [contact] [contact]

e-mail: [contact]

Investigator Reporting Responsibilities

The conduct of the study will comply with all FDA safety reporting requirements. Serious Adverse Events Reporting: The principle investigator has the obligation to report all serious adverse events to the University of Texas M. D. Anderson Cancer Center (MDACC) IRB via the Office of Protocol Research and also to Celgene within 24 hours.

IND Annual Reports

If the FDA has granted an IND number, it is a requirement of 21 CFR 312.33, that an annual report is provided to the FDA within 60-days of the IND anniversary date. 21 CRF 312.33 provides the data elements that are to be submitted in the report. The Annual Report should be filed with MD Anderson's ORERM, who will then forward to FDA. An additional copy should be placed in the study's Regulatory Binder and a copy must be sent to Celgene Corporation as a supporter of this study as follows.

Celgene Corporation Attn: Medical Development [name] [contact]

All adverse experience reports must include the patient number, age, sex, weight, severity of reaction (mild, moderate, severe), relationship to study drug (probably related, unknown relationship, definitely not related), date and time of administration of test medications and all concomitant medications, and medical treatment provided. The investigator is responsible for evaluating all adverse events to determine whether criteria for "serious" and as defined above are present. The investigator is responsible for reporting adverse events to Celgene as described below.

Expedited reporting by investigator to Celgene

Serious adverse events (SAE) are defined above. The investigator should inform Celgene of any SAE within 24 hours of being aware of the event. The date of awareness should be noted on the report. This must be documented on an MD Anderson SAE form. This form must be completed and supplied to MDACC IRB, ORERM and Celgene within 24 hours/1 business day at the latest on the following working day. The initial report must be as complete as possible, including details of the current illness and (serious) adverse event, and an assessment of the causal relationship between the event and the investigational product(s). Information not available at the time of the initial report (e.g., an end date for the adverse event or laboratory values received after the report) must be documented on a follow-up MD Anderson SAE form. A final report to document resolution of the SAE is required. The Celgene protocol number (RV-LYM-PI-0247 should be included on SAE reports to Celgene. A copy of the fax transmission confirmation of the SAE report to Celgene should be attached to the SAE and retained with the patient records.

Report of Adverse Events to the Institutional Review Board

The principal Investigator is required to notify his/her Institutional Review Board (IRB) of a serious adverse event according to institutional policy.

Sponsor Reporting to the FDA

Adverse drug reactions that are Serious, Unlisted/unexpected, and at least possibly associated to the drug, and that have not previously been reported in the Investigators

brochure, or reference safety information document should be reported promptly to the Food and Drug Administration (FDA) in writing by each investigator/physician engaged in clinical research. A clear description of the suspected reaction should be provided along with an assessment as to whether the event is drug or disease related.

The sponsor shall notify the FDA by telephone or by fax of any unexpected fatal or life threatening experience associated with the use of the drug. As soon as possible, but no later than 7 calendar days after the sponsors initial receipt of the information. Each phone call or fax shall be transmitted to the FDA new drug review division in the Center for Drug Evaluation and Research or the product review division in the Center for Biologics Evaluation and Research that has responsibility for review of the IND if applicable.

Adverse event updates/IND safety reports

Celgene shall notify the Investigator via an IND Safety Report of the following information:

- Any AE associated with the use of study drug in this study or in other studies that is both serious and unexpected.
- Any finding from tests in laboratory animals that suggests a significant risk for human subjects including reports of mutagenicity, teratogenicity, or carcinogenicity.

The Investigator shall notify his/her IRB/EC promptly of these new serious and unexpected AE(s) or significant risks to subjects.

The Investigator must keep copies of all AE information, including correspondence with Celgene and the IRB/EC, on file.

7. Response Criteria

Baseline lesion assessments will be measured. At least 1 lesion greater than 1.5 cm must be documented during screening as per Section 2, Schedule of Study Assessments.

Efficacy assessments are scheduled to occur per the Schedule of Study Assessments, Section 2. Assessments for response will be done at approximately day 1 of every cycle. Response will also be done using CT scans, PET-CT and bone marrow biopsy after 3, 6, 9 and cycle 12.

Response and progression will be evaluated in this study using the International workshop standardized response criteria for non-Hodgkin's lymphomas (IWG) (23).

-and-

Instructions for interpreting response criteria for lesion evaluation and best overall response may be found in Appendix D, International workshop standardized response criteria for non-Hodgkin's lymphomas (IWG).

8. Protocol Amendments/Deviations

Protocol amendments

Any amendment to this protocol must be agreed to by the Principal Investigator and reviewed by Celgene. Amendments should only be submitted to IRB/EC after consideration of Celgene review. Written verification of IRB/EC approval will be obtained before any amendment is implemented.

Protocol deviations

When an emergency occurs that requires a deviation from the protocol for a subject, a deviation will be made only for that subject. A decision will be made as soon as possible to determine whether or not the subject (for whom the deviation from protocol was effected) is to continue in the study. The subject's medical records will completely describe the deviation from the protocol and state the reasons for such deviation. In addition, the Investigator will notify the IRB/EC in writing of such deviation from protocol.

9. Data Management

Analyses and Reporting

Data will be analyzed and reported after all subjects have been assessed for overall response after 3 cycles. All subsequent data collected will be analyzed and reported in a follow-up clinical report.

Study monitoring and auditing

Investigator responsibilities

Investigator responsibilities are set out in the ICH guideline for Good Clinical Practice (GCP) and in the US Code of Federal Regulations.

Investigators must enter study data into MDACC's PDMS. The Investigator will permit study-related monitoring visits and audits by MDACC's ORERM, Celgene or its representatives, IRB/EC review, and regulatory inspection(s) (e.g., FDA, EMEA, TPP), providing direct access to the facilities where the study took place, to source documents, to CRFs, and to all other study documents.

The Investigator, or a designated member of the Investigator's staff, must be available at some time during monitoring visits to review data and resolve any queries and to allow direct access to the subject's records (e.g., medical records, office charts, hospital charts, and study related charts) for source data verification. The data collection must be

completed prior to each visit and be made available to MDACC ORERM and the Celgene representative so that the accuracy and completeness may be checked.

The Investigator will be responsible for reviewing the data and determining the stopping rule.

10. Biostatistical Analysis

Overview

This is an open label, phase II clinical trial to evaluate the efficacy and safety of Lenalidomide given in combination with Ritximab to patients with indolent non-Hodgkin's lymphoma.

Datasets to be analyzed

Statistical Methodology

The trial consists of 4 parallel patient cohorts. Using dose schedule A we will enroll 50 patients with follicular lymphoma (cohort 1) and 30 patients with marginal zone lymphoma (cohort 2). We will enroll 45 patients with small lymphocytic lymphoma (cohort 3). We will also enroll 30 patients with follicular lymphoma patients and treat them with dosing schedule B (cohort 4). This will allow the investigators to better characterize and define possible differences in the response rate and toxicity profiles for each of the study subgroups.

The overall response, denoted as OR (to be assessed at the end of 3 cycles), and toxicity (to be assessed at the end of the first cycle) will be monitored simultaneously for each of the subgroups separately using the Bayesian approach of Thall, Simon, Estey (1995, 1996) as extended by Thall and Sung (1998). Toxicity is defined as any grade 3 or 4 nonhematologic toxicity.

Cohort 1: For the subgroup of patients with follicular lymphoma and treated with dosing schedule A, historical data on similar patients show an overall response rate of 70% and toxicity rate of 20%. However, the information was down-weighted to reflect the same marginal OR and toxicity rates in 10 patients. Independence was assumed between OR and toxicity. It is expected for the current trial that the two-drug combination will improve the OR rate to 80% while the toxicity rate is maintained at 30%. A sample size of 50 patients ensures that, if the trial is not terminated early, a posterior 90% credibility interval for overall response rate will have width of 0.19 at most, under the assumption of an 80% of overall response rate. The probabilities of OR and toxicity for the historical data are modeled by beta distributions (Beta(7, 3) and Beta(2, 8), respectively). The prior probabilities of OR and toxicity for the experimental regimen are also modeled by beta distributions

(Beta(1.4, 0.6)) and Beta(0.4, 1.6), respectively), which have the same *means* as the corresponding beta distributions for the historical data. Denoting the historical probabilities of overall response rate and toxicity rate by {p(OR,H), p(TOX,H)}, the following decision criteria will be applied:

- 1) Let E correspond to the experimental treatment, stop if $Prob\{p(OR,H) + \delta_{OR} > p(OR,E) \mid data\} > 0.90$, where $\delta_{OR} = 0.1$
- 2) Stop if Prob{p(TOX,H) + δ_{TOX} < p(TOX,E)| data}>0.90, where δ_{TOX} =0.1

Patients will be monitored according to the following stopping boundaries for overall response and toxicity.

overall response and toxicity.	•	
Number of patients evaluated	Recommend stopping if ≤ OR observed	Recommend stopping if ≥ toxicity observed
5	2	4
10	5	7
15	8	9
20	11	11
25	14	14
30	17	16
35	20	18
40	23	21
45	26	23
50	29	25

The operating characteristics are summarized in the following table (based on simulations from 10,000 trials).

True Toxicity Rate	True OR Rate	Prob(stop the trial early)
0.10	0.60	0.71
	0.70	0.31
	0.80	0.08
	0.90	0.01
0.20	0.60	0.71
	0.70	0.32
	0.80	0.09
	0.90	0.02
0.30	0.60	0.72
	0.70	0.35
	0.80	0.13
	0.90	0.06
0.40	0.60	0.78
	0.70	0.49
	0.80	0.32
	0.90	0.27
0.50	0.60	0.91
	0.70	0.78
	0.80	0.71
	0.90	0.68

Cohort 2: For the subgroup of patients with marginal zone lymphoma and treated with dosing schedule A, historical data on similar patients show an overall response

rate of 70% and toxicity rate of 20%. However, the information was down-weighted to reflect the same marginal OR and toxicity rates in 10 patients. Independence was assumed between OR and toxicity. It is expected for the current trial that the two-drug combination will improve the OR rate to 80% while the toxicity rate is maintained at 30%. A sample size of 30 patients ensures that, if the trial is not terminated early, a posterior 90% credibility interval for overall response rate will have width of 0.23 at most, under the assumption of an 80% of overall response rate. The probabilities of OR and toxicity for the historical data are modeled by beta distributions (Beta(7, 3) and Beta(2, 8), respectively). The prior probabilities of OR and toxicity for the experimental regimen are also modeled by beta distributions (Beta(1.4, 0.6) and Beta(0.4, 1.6), respectively), which have the same means as the corresponding beta distributions for the historical data. Denoting the historical probabilities of overall response rate and toxicity rate by {p(OR,H), p(TOX,H)}, the following decision criteria will be applied:

- 3) Let E correspond to the experimental treatment, stop if $Prob\{p(OR,H) + \delta_{OR} > p(OR,E) \mid data\} > 0.90$, where $\delta_{OR} = 0.1$
- 4) Stop if Prob{p(TOX,H) + δ_{TOX} < p(TOX,E)| data}>0.90, where δ_{TOX} =0.1

Patients will be monitored according to the following stopping boundaries for overall response and toxicity.

Number of patients evaluated	Recommend stopping if ≤ OR observed	Recommend stopping if ≥ toxicity observed
5	2	4
10	5	7
15	8	9
20	11	11
25	14	14
30	17	16

The operating characteristics are summarized in the following table (based on simulations from 10.000 trials).

True Toxicity Rate	True OR Rate	Prob(stop the trial early)
0.10	0.60	0.62
	0.70	0.29
	0.80	0.08
	0.90	0.01
0.20	0.60	0.62
	0.70	0.29
	0.80	0.09
	0.90	0.02
0.30	0.60	0.64
	0.70	0.33
	0.80	0.13
	0.90	0.06
0.40	0.60	0.70
	0.70	0.44
	0.80	0.27
	0.90	0.22
0.50	0.60	0.82

0.70	0.66
0.80	0.56
0.90	0.52

Cohort 3: For the subgroup of patients with small lymphocytic lymphoma, historical data on similar patients show an overall response rate of 50% and toxicity rate of 20%. However, the information was down-weighted to reflect the same marginal OR and toxicity rates in 10 patients. Independence was assumed between OR and toxicity. It is expected for the current trial that the two-drug combination will improve the OR rate to 60% while the toxicity rate is maintained at 30%. A sample size of 45 patients ensures that, if the trial is not terminated early, a posterior 90% credibility interval for overall response rate will have width of 0.23 at most, under the assumption of an 60% of overall response rate. The probabilities of OR and toxicity for the historical data are modeled by beta distributions (Beta(5, 5) and Beta(2, 8), respectively). The prior probabilities of OR and toxicity for the experimental regimen are also modeled by beta distributions (Beta(1, 1) and Beta(0.4, 1.6), respectively), which have the same means as the corresponding beta distributions for the historical data. Denoting the historical probabilities of overall response rate and toxicity rate by {p(OR,H), p(TOX,H)}, the following decision criteria will be applied:

- 5) Let E correspond to the experimental treatment, stop if $Prob\{p(OR,H) + \delta_{OR} > p(OR,E) \mid data\} > 0.90$, where $\delta_{OR} = 0.1$
- 6) Stop if Prob{p(TOX,H) + δ_{TOX} < p(TOX,E)| data}>0.90, where δ_{TOX} =0.1

Patients will be monitored according to the following stopping boundaries for overall response and toxicity.

Number of patients evaluated	Recommend stopping if ≤ OR observed	Recommend stopping if ≥ toxicity observed
5	1	4
10	3	7
15	5	9
20	7	11
25	8	14
30	10	16
35	12	18
40	14	21
45	16	23

The operating characteristics are summarized in the following table (based on simulations from 10,000 trials).

True Toxicity Rate	True OR Rate	Prob(stop the trial early)
0.10	0.40	0.65
	0.50	0.32
	0.60	0.12
	0.70	0.04
0.20	0.40	0.65
	0.50	0.33

	0.60	0.13
	0.70	0.04
0.30	0.40	0.67
	0.50	0.36
	0.60	0.17
	0.70	0.09
0.40	0.40	0.74
	0.50	0.49
	0.60	0.34
	0.70	0.28
0.50	0.40	0.88
	0.50	0.76
	0.60	0.69
	0.70	0.66

Cohort 4: For the subgroup of patients with follicular lymphoma and treated with dosing schedule B, historical data on similar patients show an overall response rate of 70% and toxicity rate of 20%. However, the information was down-weighted to reflect the same marginal OR and toxicity rates in 10 patients. Independence was assumed between OR and toxicity. It is expected for the current trial that the twodrug combination will improve the OR rate to 80% while the toxicity rate is maintained at 30%. A sample size of 30 patients ensures that, if the trial is not terminated early, a posterior 90% credibility interval for overall response rate will have width of 0.23 at most, under the assumption of an 80% of overall response rate. The probabilities of OR and toxicity for the historical data are modeled by beta distributions (Beta(7, 3) and Beta(2, 8), respectively). The prior probabilities of OR and toxicity for the experimental regimen are also modeled by beta distributions (Beta(1.4, 0.6) and Beta(0.4, 1.6), respectively), which have the same means as the corresponding beta distributions for the historical data. Denoting the historical probabilities of overall response rate and toxicity rate by {p(OR,H), p(TOX,H)}, the following decision criteria will be applied:

- 1) Let E correspond to the experimental treatment, stop if $Prob\{p(OR,H) + \delta_{OR} > p(OR,E) \mid data\} > 0.90$, where $\delta_{OR} = 0.1$
- 2) Stop if Prob{p(TOX,H) + δ_{TOX} < p(TOX,E)| data}>0.90, where δ_{TOX} =0.1

Patients will be monitored according to the following stopping boundaries for overall response and toxicity.

Number of patients evaluated	Recommend stopping if ≤ OR observed	Recommend stopping if ≥ toxicity observed
5	2	4
10	5	7
15	8	9
20	11	11
25	14	14
30	17	16

The operating characteristics are summarized in the following table (based on simulations from 10.000 trials).

True Toxicity Rate	True OR Rate	Prob(stop the trial early)
0.10	0.60	0.62
	0.70	0.29
	0.80	0.08
	0.90	0.01
0.20	0.60	0.62
	0.70	0.29
	0.80	0.09
	0.90	0.02
0.30	0.60	0.64
	0.70	0.33
	0.80	0.13
	0.90	0.06
0.40	0.60	0.70
	0.70	0.44
	0.80	0.27
	0.90	0.22
0.50	0.60	0.82
	0.70	0.66
	0.80	0.56
	0.90	0.52

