Schedule A: Lenalidomide will be administered orally at 20 mg total daily dose on days 1 to 21 of a 28 day cycle in patients with follicular and marginal zone lymphoma. Following cycle 3, if patients fail to show a response (partial or complete) the dose will be increased to 25mg/day. Patients with a diagnosis of small lymphocytic lymphoma (SLL) will begin at a dose of 10 mg total daily on days 1 to 21 of a 28 day cycle. This dose will be escalated by 5mg every 28 days up to 20mg if no toxicity is encountered. If no response is observed by cycle 3, the dose will be increased to 25 mg. (see dose modification for lenalidomide table). A single 375 mg/m2 intravenous dose of rituximab will be given at day 1 of every cycle.

Schedule B: Lenalidomide will be administered orally at 20 mg total daily dose on days 2 to 22 of a 28 day cycle in patients with follicular lymphoma. Following cycle 3, if patients fail to show a response (partial or complete) the dose will be increased to

25mg/day. Patients with a diagnosis of small lymphocytic lymphoma (SLL) will begin at a dose of 10 mg total daily on days 2 to 22 of a 28 day cycle. This dose will be escalated by 5mg every 28 days up to 20mg if no toxicity is encountered. If no response is observed by cycle 3, the dose will be increased to 25 mg. (see dose modification for lenalidomide table). A single 375 mg/m2 intravenous dose of rituximab will be given at day 1, 8,15, and 22 of cycle 1 and on day 1 of every subsequent cycle. In the absence of progression or toxicity, patients will remain on treatment for a total of 12 months. If patients attain a complete response following cycle 6 or 9, lenalidomide will be reduced to 10mg daily for the remaining cycles with the same dosing schedule of rituximab and lenalidomide as described above."

Patients that have documented clinical benefit and no evidence of progression of disease can remain on treatment for a total of 12 months. Treatment will be continued at the cycle 6 dose level with the same dosing schedule of rituximab and lenalidomide as described above.

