Several phase II studies have shown activity with lenalidomide in CLL. Higher doses (25mg) have been associated with increased toxicity in the form of an increased incidence of tumor flare and tumor lysis syndrome (TLS).27,28 Tumor flare has also been correlated with response and may be associated with lenalidomide efficacy. 29 However, lower doses (10mg) appear to be better tolerated and have been associated with fewer cases of tumor flare. Ferrajoli et al treated 35 patients with CLL with a starting dose of 10mg daily for 28 days with a dose escalation to 25mg as tolerated. There were no cases of tumor lysis reported, and only 12% of patients developed tumor flare. The median dose level was 10mg. 30 In another phase II trial with lenalidomide in CLL, 2 out of the first 25 patients experienced TLS at the initial starting dose level (25mg). The study was modified to begin at a lower starting dose and none of the 16 patients who started on the 10mg dose level experienced tumor lysis. The incidence of tumor flare was unchanged, but the severity of reactions decreased significantly.31

Response to therapy will be assessed after 3 cycles and after 6 cycles of chemotherapy. In patients that continue on with extended dosing beyond cycle 6, response will also be evaluated after 9 and 12 cycles of chemotherapy. If after 3 cycles of therapy, there is stable disease without progression, as defined by IWG criteria, the lenalidomide dose will be increased for a total daily dose of 25mg, or 5 mg above the current dose in patients with SLL. If there is evidence of progression of disease, the patient will discontinue study medication.

The rationale for schedule B is derived from studies in both CLL and multiple myeloma suggest a clinical benefit (response rate and PFS) with extended dosing of lenalidomide. In schedule B, the dose of lenalidomide will be reduced in responding patients on cycles 7-12 to minimize potential myelosupression with increased exposure. In addition, significant infusion reactions to rituximab have been noted to occur beyond cycle 2. Although etiology of the infusion reactions is unknown, the severity of the reaction may be potentiated by concurrent dosing of lenalidomide. Ancedotal experience suggests that starting lenalidomide on day 2 of treatment (rituximab on day 1) may lessen the observed toxicity. Dose intensification of rituximab (weekly dosing) will occur in cycle 1 to increase mean serum concentration early in treatment.

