The amount of drug to be administered will be based on BSA. Body surface area will be calculated using a standard nomogram on Cycle 1, Day 1 and at subsequent visits if the subject experiences a >5% change in body weight from the weight used for the most recent BSA calculation.

Schedule A: The planned dose of lenalidomide for patients with follicular lymphoma and marginal zone lymphoma is 20 mg/day, orally on days 1-21 followed by 7 days rest (28 day cycle). Following cycle 3, if patients fail to show a response (partial or complete) the dose will be increased to 25 mg/day.

Schedule B: Lenalidomide will be administered orally at 20 mg total daily dose on days 2 to 22 of a 28 day cycle in patients with follicular lymphoma. Following cycle 3, if patients fail to show a response (partial or complete) the dose will be increased to

25mg/day. Patients with a diagnosis of small lymphocytic lymphoma (SLL) will begin at a dose of 10 mg total daily on days 2 to 22 of a 28 day cycle. This dose will be escalated by 5mg every 28 days up to 20mg if no toxicity is encountered. If no response is observed by cycle 3, the dose will be increased to 25 mg. (see dose modification for lenalidomide table). A single 375 mg/m2 intravenous dose of rituximab will be given at day 1, 8,15, and 22 of cycle 1 and on day 1 of every subsequent cycle. In the absence of progression or toxicity, patients will remain on treatment for a total of 12 months. If patients attain a complete response following cycle 6 or 9, lenalidomide will be reduced to 10mg daily for the remaining cycles with the same dosing schedule of rituximab and lenalidomide as described above.

Dosing will be at approximately the same time each day. The planned dose of lenalidomide for patients with SLL is 10 mg/day, orally on days 1-21 followed by 7 days rest (28 day cycle). If no toxicities are encountered, the dose of lenalidomide in patients with SLL will be increased by 5 mg with each cycle up to 20 mg/day. Following cycle 3, if patients fail to show a response (partial or complete) the dose will be increased to 25 mg/day. Only one cycle of study drug will be supplied to the patient each cycle.(for dose modification guidelines, see Table 2: Dose modification for Lenalidomide) Only one cycle of study drug will be supplied to the patient each cycle.

If a dose of lenalidomide is missed, it should be taken as soon as possible on the same day. If it is missed for the entire day, it should not be made up.

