Allergic reaction or hypersensitivity Grade 2-3	 Hold (interrupt) dose. Follow at least weekly. If the toxicity resolves to ≤ grade 1 prior to Day 21 restart at next lower dose level and continue the cycle until Day 21. 	Omit lenalidomide for the remainder of the cycle.
Grade 4	Discontinue lenalidomide study drug.	Discontinue lenalidomide study drug

Table 2: Dose Modification	n for Lenalidomide	
NCI CTC Toxicity Grade	Day 2-14 of Cycle	≥Day 15 of Cycle
Venous thrombosis/embolism ≥ Grade 3	 Hold (interrupt) dose and start anticoagulation; restart at investigator's discretion (maintain dose level). 	Omit lenalidomide for remainder of cycle. Anticoagulation measures as described in Conncomitant therapy section below.
other non-hematologic toxicity assessed as Lenalidomide-related ≥ Grade 3	 Hold (interrupt) dose. Follow at least weekly. If the toxicity resolves to ≤ grade 2 prior to Day 21 restart at next lower dose level and continue the cycle until Day 21. 	Omit lenalidomide for remainder of cycle.
Hyperthyroidism or hypothyroidism	Omit lenalidomide for remainder of cycle, evaluate etiology, and initiate appropriate therapy. Restart lenalidomide next cycle (decrease dose by one dose level).	Omit lenalidomide for remainder of cycle, evaluate etiology, and initiate appropriate therapy. Restart lenalidomide next cycle (decrease dose by one dose level).

[†] If patient had low baseline platelets due to prior to study entry, dose reduction not required.

Dose Escalation

In schedule B, all patients in a complete response will reduce lenalidomide to 10mg daily on cycles 7-12.

If after 3 cycles of therapy, there is stable disease without evidence of progression as defined by IWG criteria, the lenalidomide dose will be increased to 25 mg per day (dose level +1) or 5 mg above the current dose in patients with SLL. The initiation of the next cycle will only be initiated if there is no evidence of toxicity as outlined above in the Instructions for Initiation of a New Cycle.

Treatment compliance

Subjects will be asked to maintain a diary to record the drug administration.

Prohibited concomitant therapy

Concomitant use of sargramostim (GM-CSF), other anti-cancer therapies, including radiation, thalidomide, or other investigational agents is not permitted while subjects are receiving study drug during the treatment phase of the study.

Discontinuation of Study Treatment

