In Schedule A, treatment will continue until six cycles or the occurrence, if it is determined by the treating physician that the patient will derive clinical benefit from

extended dosing. **In schedule B**, all patients will continue until 12 cycles or the occurrence of any of the following events.

Treatment with study drug is to be discontinued when any of the following occurs:

- Lack of therapeutic effect
- Adverse event(s) that, in the judgment of the Investigator, may cause severe or permanent harm or which rule out continuation of study drug.
- Major violation of the study protocol.
- Withdrawal of consent
- Lost to follow up
- Death
- Suspected pregnancy

Follow-Up

Subjects who discontinue treatment for any reason, will be followed for 6 months. Subjects will undergo a safety assessment approximately 28 days post the last dose of study drug. In addition, off study evaluations, such as recording subsequent therapy, per the Schedule of Assessments will be done. Following completion of chemotherapy, patients will be evaluated every 3 months for one year, every 6 months for 1 year and then yearly with CT of neck, thorax, abdomen and pelvis and other studies as recommend by the treating physician.

Correlative Studies:

The mechanism of action, as well as the effect on the target microenvironment of the combination of lenalidomide and rituximab is poorly understood. In vitro, lenalidomide has been shown to increase recruitment and activation of immune effector cells and potentially repair T cell recognition and killing of malignant cells. By measuring levels of immune effector cells in accessible lesions, and comparing these with pre-treatment biopsies, we will learn about potential mechanisms of action of lenalidomide in untreated NHL.

Using peripheral blood samples, we will measure the number and function of immune effector cell subsets on day 1 of cycle 1 (allowed up to 48 hours prior to treatment), day 1 prior to treatment on cycle 2, day 15 of cycle 2, and on day 28 (+/- 3 days) of cycle 6. We will also measure gene expression on PBMCs prior to treatment on day 1 (allowed up to 48 hours prior to treatment) and on day #15 of cycle 2.

An elective core needle biopsy of an accessible tumor will be obtained with the patient's consent on day 18 of cycle 1. The tumor composition will be examined for infiltration and levels of non-malignant B-cells, activated NK cells, and T-cell subsets.

6. Adverse events

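### After cycle 3, two parts of Section 5 escalate every non-responder with no exception for progression, another takes progressors off, and the mandatory stop list does not settle which applies

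*Combined protocol and SAP*

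**What the plan says.** All the rules are in Section 5, Investigational Plan.

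- **Overall design, schedule paragraphs.** For follicular and marginal zone lymphoma on Schedule A: "Following cycle 3, if patients fail to show a response (partial or complete) the dose will be increased to 25mg/day". The Schedule B paragraph has the same rule for follicular lymphoma. For SLL, under both schedules: "If no response is observed by cycle 3, the dose will be increased to 25 mg". Schedule B patients otherwise stay on for 12 months unless they progress or have toxicity.
- **Overall design, response-assessment paragraph.** The increase is limited to stable disease: "If after 3 cycles of therapy, there is stable disease without progression, as defined by IWG criteria, the lenalidomide dose will be increased". Then: "If there is evidence of progression of disease, the patient will discontinue study medication".
- **Drug Administration.** The broad rule again: "Following cycle 3, if patients fail to show a response (partial or complete) the dose will be increased to 25 mg/day".
- **Dose Escalation.** The narrow rule again: "If after 3 cycles of therapy, there is stable disease without evidence of progression as defined by IWG criteria, the lenalidomide dose will be increased".
- **Discontinuation of Study Treatment.** The list opens with mandatory wording: "Treatment with study drug is to be discontinued when any of the following occurs". Its entries include lack of therapeutic effect, which is not defined. Disease progression has no entry of its own.

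**The concern.** A patient with progressive disease at the cycle 3 assessment has, by definition, not shown a partial or complete response. The broad rule therefore covers that patient and raises the dose, while the response-assessment paragraph takes the same patient off study medication. These are opposite mandatory instructions for one patient at one assessment.

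The list that should settle the matter does not name progression. Its nearest entry can be read narrowly, as progression, or widely, as any absence of response. The wide reading would stop a stable patient whom two other paragraphs escalate.

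Who receives the higher dose, and who stays on treatment long enough to respond at cycle 6, 9 or 12, could then depend on which paragraph the treating physician follows. The trial is open label, so that choice is made with the patient's course in view. There is a safety side too: Overall design itself links 25 mg to more tumor flare and tumor lysis in CLL.

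**Working it through.** No planned figure is in dispute, so there is none to reproduce. The check sets the rules side by side and then counts the patients who could be exposed to them.

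**Step 1. What each place says for a patient without CR or PR after cycle 3**

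| Place in Section 5 | Stable disease | Progressive disease |
|---|---|---|
| Overall design, schedule paragraphs | Increase | Increase, no exception stated |
| Overall design, response-assessment paragraph | Increase | Discontinue |
| Drug Administration | Increase | Increase, no exception stated |
| Dose Escalation | Increase | Not stated |
| Discontinuation of Study Treatment | Stop only if judged to lack effect | Not named; stop only if judged to lack effect |

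The progressive-disease column contains a literal contradiction (increase against discontinue). The stable-disease column is consistent in four rows. The fifth conflicts only under one reading of an undefined term.

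**Step 2. Which analyses come before the decision**

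Section 10 reads toxicity at the end of cycle 1 and overall response at the end of cycle 3. The dose decision acts after both. Section 9 has the first analysis and report follow the cycle 3 assessments. The stopping boundaries and the operating characteristics therefore do not depend on which rule is followed.

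Three things come after the decision:
- Response is reassessed after cycles 6, 9 and 12. Section 4 gives the primary endpoint as the number of CR and PR without a time point.
- The Analysis Plan includes time-to-event summaries, and the synopsis (though not Section 4) lists progression-free survival as primary.
- Exposure to the higher dose is set by the decision itself.

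**Step 3. How many patients could be involved**

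Inputs are from Section 10: cohort sizes 50 (follicular, Schedule A), 30 (marginal zone), 45 (SLL) and 30 (follicular, Schedule B). Target response rates are 80%, 80%, 60% and 80%. Historical rates are 70%, 70%, 50% and 70%.

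Expected non-responders = cohort size × (1 − response rate), summed over cohorts.

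- Target rates: 50 × 0.20 + 30 × 0.20 + 45 × 0.40 + 30 × 0.20 = 10 + 6 + 18 + 6 = 40; 40/155 = 26%.
- Historical rates: 50 × 0.30 + 30 × 0.30 + 45 × 0.50 + 30 × 0.30 = 15 + 9 + 22.5 + 9 = 55.5, about 56; 55.5/155 = 36%.

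These totals combine stable and progressive disease. The documents give no split at cycle 3, so neither group can be sized separately.

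**The case against.** The strongest reply is that the intent can be recovered. The rule for progression is explicit and more specific than the broad rule, and it stands in the same Overall design section. The escalation trigger is stated twice as stable disease without progression. Schedule B treatment is also conditional on no progression. This stands as a reason to rate the point as a wording conflict and not a design failure. It does not remove the conflict. Drug Administration repeats the broad rule without an exception, Dose Escalation is silent on progressors, and the mandatory list does not name progression.

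Four stronger readings are tempting, and the documents do not support them.

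- *The plan orders stable patients to stop.* No text equates stable disease with lack of therapeutic effect. Section 5 escalates stable patients or keeps them on, the background counts stable disease towards tumor control, and the entry may be how the list covers progression. What remains is an undefined mandatory criterion.
- *The Bayesian monitoring is compromised.* It is not, because both monitored outcomes are read before the dose decision.
- *Patients who stop without progression have no IWG category or progression date.* Section 2 marks an IWG response assessment at discontinuation and CT in follow-up. The Follow-Up text gives 6 months for patients who discontinue and a longer schedule after completion. The length is therefore unclear, but imaging does not end with treatment.
- *Forty patients receive contradictory instructions.* The literal contradiction concerns progressors only, and they are an unknown part of the 40.

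**Conclusion.** The point holds as an inconsistency in the cycle 3 rules. For progressive disease, Section 5 contradicts itself on the text. For stable disease, it contains a mandatory stop criterion that is undefined and could be applied against the escalation rule.

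The number affected is at most the number of cycle 3 non-responders: an expected 40 of 155 at the target rates and about 56 at the historical rates. This assumes full accrual, every patient assessed at cycle 3, and true response rates equal to the plan's own figures.

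The consequences are confined to later response, time-to-event summaries and exposure to the higher dose. How far those results would move cannot be estimated from the documents. The correction is worth making because it is specific and cheap and bears on safety. The size of the SLL dose step also differs between these paragraphs, but that is a separate matter and is not counted here.

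**What to change.** Reconcile Overall design, Drug Administration, Dose Escalation and Discontinuation of Study Treatment:

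1. Write every escalation, continuation and stopping rule in the same named IWG categories (CR, PR, stable disease, progressive disease).
2. State in the discontinuation list whether IWG progression is a discontinuation event.
3. Tie the lack-of-effect entry to an IWG category and a time point, or remove it.

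Which category escalates, continues or stops is the sponsor's clinical decision, and this review does not propose one.

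The cost is a wording amendment with no added procedures. The IWG category at discontinuation needs no new recording, since the Schedule of Study Assessments already provides for it. The downside is slightly less room for physician discretion.
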